8.2.2. Defining the variables of interest

Table 1. Variables of interest

Treatment Outcomes
Primary outcome: VAS ratings
Secondary outcomes: Self-reported patient questionnaires (SFMPQ, PDI, BPI, MBM, FSQ)
Exploratory outcomes: Self-reported patient questionnaires (PainDETECT, EQ-5D, HADS, CSQ, PROMIS SD), QST measures (generalized mechanical sensitivity, vibration sensitivity, pressure-pain sensitivity, TS and CPM)

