2. SCHEDULE OF EVALUATIONS

	Screening/ enrollment visit	Pre- implantation visit ^a	First trial-phase visit	Second trial-phase visit	Third trial-phase visit
	Visit 1	Visit 2	Visit 3	Visit 4	Visit 5
Informed Consent	X				
Hospital Anxiety and Depression Scale (HADS)	X	X	X		
EQ-5D Health Questionnaire	X	X	X		
Demographics	X				
Concomitant Medications	X	X	X	X	X
Socio-demographics	X				
Brief Pain Inventory (BPI)	X	X	X	X	X
Coping Strategies Questionnaire (CSQ)	X	X	X	X	X
Michigan Body Map (MBM)	X	X	X	X	X
PainDETECT	X	X	X	X	X
Pain Disability Index (PDI)	X	X	X	X	X
Fibromyalgia Survey Questionnaire (FSQ)	X	X	X	X	X
Patient-Reported Outcomes Measurement Information System Sleep Disturbance Short Form Questionnaire (PROMIS-SD)	X	X	X	X	X
Short Form McGill Pain Questionnaire (SFMPQ)	X	X	X	X	X
Visual Analog Scale (VAS) – included in SFMPQ	X	X	X	X	X
Vitals (heartrate, blood pressure, respiration rate, blood temperature), height and weight	X	X	X	X	X
Multimodal Automated Sensory Test (MAST)	b	X	X	X	X
Vibrometer Test	b	X	X	X	X
Algometer Test	b	X	X	X	X
PinPrick Test	b	X	X	X	X
Conditioned Pain Modulation (CPM) Test	b	X	X	X	X
Randomization			c		
Treatment (Burst-SCS/Sham SCS)			d	X	X
Adverse Events	X	X	X	X	X

^aPre-implantation visit may also occur on the same day as the screening/enrollment visit

^bFamiliarization only

^cRandomization will occur at the end of Visit 3

^dTreatment will begin at the end of Visit 3

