5. SPECIFIC AIMS/HYPOTHESES

5.1 To identify the treatment effects of Burst-SCS (Aim 1).

The goal of this aim is to determine the **pain-relieving effects of Burst-SCS**. In a randomized, double-blind, placebo-controlled, crossover study, we will compare the pain-relieving effects of Burst-SCS to sham (no) SCS in patients receiving Burst-SCS as part of their standard clinical care for chronic pain management. The primary outcome measure will be the change in patient-reported ratings of pain intensity (measured by the Visual Analog Scale, VAS).¹⁴ Secondary outcome measures will be related to the change in patient-reported ratings of pain quality [(measured by Pain Disability Index (PDI)²³ and Short Form McGill Pain Questionnaire (SFMPQ)],²⁴ pain severity (measured by Brief Pain Inventory, BPI),²⁵ pain spread (measured by Michigan Body Map, MBM),²⁶ and pain centralization (measured by Fibromyalgia Survey Criteria, FSQ).²⁷ Exploratory outcome measures will be related to the change in patient-reported ratings of affect (depression, anxiety), fatigue, sleep interference, catastrophizing, physical function, and overall quality of life. **We hypothesize that Burst-SCS will provide superior pain relief in patients as compared to sham SCS.**

5.2 To identify the therapeutic mechanisms of Burst-SCS (Aim 2).

The goal of this aim is to determine the **potential therapeutic mechanisms of action of Burst-SCS**. We will perform detailed clinical testing in the patients from Aim 1 using a series of quantitative sensory testing (QST) measures. We will assess sensitivity to non-painful vibratory stimuli and painful pressure stimuli. We will assess pain perception in response to sequential stimuli of equal physical strength (temporal summation or TS).²⁸ We will also determine the efficiency of (supraspinal) descending pain inhibition by measuring pain thresholds subsequent to the application of an acute conditioning stimulus (conditioned pain modulation or CPM).^{29,30} **We hypothesize that patients who respond to Burst-SCS will show decreased vibration and decreased pressure-pain sensitivity, reduced TS, and improved inhibitory CPM. Alternatively, patients who do not respond to Burst-SCS will demonstrate no changes or worsening of QST outcomes.**

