6. PROPOSED STUDY METHODS

6.1 Study Design

The study design is a **randomized, double-blind, placebo-controlled, crossover study design**. Subjects will participate in up to five research visits (**Figure 1**). During the first visit, we will screen chronic pain patients who have already been selected to receive a temporary externalized trial of Burst-SCS from their own doctors as part of their standard clinical care. During the second visit, we will perform pre-operative baseline assessment in the subjects prior to implantation of their SCS electrode arrays. Following lead implantation, and during the externalized “**trial phase**” of Burst-SCS, we will randomize subjects to receive either 24 hours of clinically-effective Burst-SCS followed by 24 hours of sham SCS or vice versa (crossover design). We will perform assessments before the start of the

randomization (visit 3), and at the end of each 24-hour period (visits 4 and 5). **Note:** Empirical evidence suggests that maximal pain relief can be measured within 24 hours.³¹⁻³⁴ Patients also clearly state that their pain returns within a matter of seconds to a maximum of few hours when the stimulation is switched off.¹⁹ Therefore, the plan for the crossover to occur after 24 hours of the initial treatment should not only be sufficient to detect significant differences in pain relief, but should also allow sufficient wash-out time for the initial treatment. Furthermore, the 24-hour stimulation window will allow us to complete the experiment within a reasonable timeframe. On the contrary, increasing the crossover period to longer than 24 hours could lead to potential confounds, such as patients increasing their medications and/or patient withdrawal because sham SCS may not provide adequate pain relief.

[figure not shown]

Figure 1. Schematic of the study design. Testing time-points are denoted by *

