6.3.2 Exclusion criteria

- Subjects who are pregnant- as determined by verbal report or chart review.
- Subjects with current, habitual, or previous use within the last 12 months of artificial nails, nail enhancements, or nail extensions that cover any portion of either thumbnail. Exceptions, including brief and/or occasional use, may be permissible at the discretion of the principal investigator (PI).
- Subjects who are unable or unwilling to cooperate with clinical testing.
- Subjects having any impairment, activity or situation that, in the judgement of the study coordinator or PI, would prevent satisfactory completion of the study protocol.

If patients meet eligibility criteria, we will ask them (during the screening visit) if they would like to enroll in the study. If they enroll, we will ask them to sign an informed consent form/document, and invite them to be part of various study visits (included in **2. Schedule of Evaluations**). We will also ask patients about their medical, social and psychiatric history. We will additionally assess patients' psychological status (e.g. anxiety, depression) using self-reported patient questionnaires/surveys (e.g. EuroQol questionnaire, EQ-5D³⁵ and Hospital Anxiety and Depression Scale, HADS- **resource included in section 29 of the IRB application**).³⁶ If patients meet criteria for extreme anxiousness or depression (as indicated in the EQ-5D questionnaire or an equivalent score of 11-21 on HADS) we will offer/provide them with a "Depression Resource Handout" (**resource included in section 44 of the IRB application**). However, patients can still continue their participation in the study. We will also collect patients' vital signs (heart rate, blood pressure, respiration rate, and body temperature), height, and weight during the screening visit, and also during each subsequent visit. Furthermore, we will collect other additional information (e.g. demographics, sociodemographics, concomitant medications- **resource included in section 29 of the IRB application**) from the patients during enrollment and during each subsequent visit (e.g. change in medications, post-QST VAS, post-QST survey- **resource included in section 29 of the IRB application**).

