7.1.3 Exploratory Outcomes

We will measure other or exploratory outcomes using several self-reported patient questionnaires (**all included in section 29 of the IRB application**) and using various QST methods (all described in section 7.2.1). We will use the PainDETECT to detect neuropathic pain components in patients.³⁸ We will use the HADS to assess anxiety and depression,³⁶ Patient Reported Outcomes Information System Sleep Disturbance Short Form questionnaire (PROMIS SD) to assess sleep interference, and Coping Strategies Questionnaire (CSQ) to assess catastrophizing in patients.³⁹ We will use the EQ-5D to characterize the patient's quality of life.³⁵ We will administer these questionnaires on paper and/or using the Qualtrics survey platform.

7.2 Assessing the therapeutic mechanisms of Burst-SCS (Aim 2).

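### HADS and EQ-5D are listed as treatment outcomes but are scheduled only before randomised treatment starts, so they can give no Burst-sham comparison

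*Combined protocol and SAP*

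**What the plan says.** Section 5.1 describes Aim 1 as a randomised, sham-controlled crossover comparison and adds: "Exploratory outcome measures will be related to the change in patient-reported ratings of affect (depression, anxiety), fatigue, sleep interference, catastrophizing, physical function". Overall quality of life completes that list. Section 7.1.3, which falls under the heading for assessing treatment effects, names the instruments: "We will use the HADS to assess anxiety and depression" and "We will use the EQ-5D to characterize the patient's quality of life". Table 1 in section 8.2.2 then lists both under its Treatment Outcomes heading: "Exploratory outcomes: Self-reported patient questionnaires (PainDETECT, EQ-5D, HADS, CSQ, PROMIS SD".

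The schedule in section 2 has one row for "Hospital Anxiety and Depression Scale (HADS") and one for "EQ-5D Health Questionnaire". Each is marked at visits 1, 2 and 3 and blank at visits 4 and 5. The footnotes to the schedule put both randomisation and the start of treatment at the end of visit 3. Section 6.1 places the assessments before "randomization (visit 3), and at the end of each 24-hour period (visits 4 and 5").

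Both instruments also have a screening role. Section 6.3.2 uses them to assess "psychological status (e.g. anxiety, depression) using self-reported patient questionnaires/surveys" and to decide who is offered a resource handout.

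**The concern.** The outcome list and the schedule do not agree. The outcome list calls for an effect of Burst-SCS on affect and quality of life; the schedule collects nothing on either after a randomised period. No analysis can repair this later, because the data would not exist.

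The only change that could be computed runs from visits 1 and 2, before implantation, to visit 3, after implantation and before randomisation. It has no sham comparator. It also spans lead implantation and the standard-care trial, in which clinicians look for the best stimulation settings (sections 6.6 and 14.2.6). Section 8.3.1 groups visit 3 with visits 4 and 5 as post-implantation for VAS and plans a similar comparison for the pain-specific questionnaires. A report that followed Table 1 could extend this to HADS and EQ-5D and present an uncontrolled change as a treatment outcome. Section 3 gives control of placebo effects as the reason for the design, so that reading would work against the trial's own purpose.

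**Working it through.** The plan states no power, SD or effect size for these outcomes, so there is no figure to reproduce. The check is a count from the schedule.

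**Inputs.** 20 patients (section 8.1); randomisation and treatment start at the end of visit 3 (section 2, footnotes); one assessment closes each randomised period, at visits 4 and 5 (section 6.1); visit marks from section 2.

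| Exploratory questionnaire | Marked at visits 1-3 | Marked at visits 4-5 | Burst-sham differences per patient |
|---|---|---|---|
| HADS | 3 | 0 | 0 |
| EQ-5D | 3 | 0 | 0 |
| PainDETECT | 3 | 2 | 1 |
| CSQ | 3 | 2 | 1 |
| PROMIS-SD | 3 | 2 | 1 |

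**Missing period-end data.**
- Possible per instrument: 20 patients x 2 visits = 40. Scheduled: 0.
- Possible for both: 40 x 2 = 80. Scheduled: 0.
- Paired differences per instrument: 0 of 20.

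**What is collected.** 20 patients x 3 visits x 2 instruments = 120 administrations, all before randomised treatment. A footnote to the schedule allows visits 1 and 2 on the same day. If the questionnaires were then given once for every patient, the count would be 20 x 2 x 2 = 80. The conclusion is the same.

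**Share affected.** 2 of 5 exploratory questionnaires. Aim 1 names six exploratory constructs (affect, fatigue, sleep interference, catastrophizing, physical function, quality of life); 2 of the 6 rest on these instruments.

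**Precision if both were added at visits 4 and 5.** For a two-period crossover adjusted for period, with equal sequence sizes, the half-width of the 95% CI in units of the SD of the within-patient difference is

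t(0.975, n - 2) / sqrt(n)

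- n = 20: 2.101 / 4.472 = 0.470
- n = 18: 0.500
- n = 16: 0.536

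The completer numbers and the equal sequences are assumptions; section 6.4 gives no allocation ratio.

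**Visit load.** Visits 2 and 3 carry 10 questionnaires: BPI, CSQ, MBM, PainDETECT, PDI, FSQ, PROMIS-SD, SFMPQ (with the VAS), HADS and EQ-5D. Visits 4 and 5 carry 10 - 2 = 8. All four visits have the same 5 QST tests, and section 1 plans about 2 hours for every visit.

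**The case against.** The strongest reply is that the blanks are deliberate. The two rows stand near the top of the schedule, apart from the other questionnaires. Section 6.3.2 uses both for screening, and section 7.1.3 says EQ-5D will characterise quality of life. On this reading Table 1 carries a loose label and no data collection was overlooked. That may well be the intention, but no section says so. Sections 5.1, 7.1.3 and 8.2.2 all call these outcomes, and section 5.1 speaks of change under an aim that compares Burst-SCS with sham. If characterisation was meant, the outcome lists need correcting.

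It can also be said that the change from visits 1 and 2 to visit 3 is a legitimate descriptive change. It is, provided it is labelled as uncontrolled. It cannot answer the question in Aim 1, and the documents do not say whether stimulation is on at visit 3.

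A third argument is that 24 hours is too short for these instruments to respond. The plan does not make it, and it does collect PROMIS-SD and CSQ after each 24-hour period.

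Finally, the harm is limited. These are exploratory measures, no specific test is written for them, and misreporting is a risk and not a certainty. That is correct and bounds the importance of the point. It does not remove the contradiction. A scrambled table is an unlikely explanation, since both rows show the same three marks while the other questionnaire rows show five.

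**Conclusion.** The concern holds. If the schedule is followed, HADS and EQ-5D give 0 of 40 period-end assessments each, and no Burst-sham difference in affect or quality of life can be estimated from them. This follows from the schedule and its footnotes and does not depend on any assumed SD, completion rate or allocation ratio; those assumptions enter only the precision figures.

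The point is confined to two exploratory questionnaires. VAS, the secondary questionnaires, the QST measures, PainDETECT, CSQ and PROMIS-SD are all scheduled at both period ends and are unaffected. The inconsistency should be resolved, but it does not threaten the primary comparison.

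**What to change.** Choose one of two options and make sections 2, 5.1, 7.1.3 and 8.2.2 agree.

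**Option 1: collect the data.** Mark HADS and EQ-5D at visits 4 and 5. Report the within-patient Burst-sham difference, adjusted for period, with a 95% CI and labelled exploratory. With a half-width of about 0.47 SD for 20 completers and 0.54 SD for 16, this supports estimation only. The cost is two more questionnaires at two existing visits, which take visits 4 and 5 from 8 to 10, the load visits 2 and 3 already carry. Patient burden rises slightly; the documents give no completion times. This helps only patients who have not yet reached visits 4 and 5.

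**Option 2: change the label.** If 24 hours is judged too short for these instruments, remove them from the treatment outcomes in 5.1, 7.1.3 and Table 1, and describe them as pre-randomisation characterisation. State that visit 3 follows implantation and the standard-care trial, so it is not a pre-implantation baseline. Report any change from visits 1 and 2 to visit 3 as descriptive and uncontrolled, and draw no conclusion about a Burst-SCS effect on affect or quality of life. The cost is a wording correction in three places.

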8.3 Data analysis

8.3.1 Treatment outcomes

We will compute VAS scores at pre-implantation (visits 1 and 2) and post-implantation (visits 3,4 and 5) to help assess percentage change in pain scores due to the effects of stimulation (Burst-SCS and sham SCS). We will also compare our VAS ratings to other clinical results available in the literature. Similarly, we will assess outcomes of pain-specific questionnaires at pre-implantation and post-implantation, and compare across all patients using appropriate statistical tests.

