1. STUDY SYNOPSIS

Study Title	Clinical characterization of burst spinal cord stimulation for chronic pain management.
Study Sponsor	Michigan Institute for Clinical & Health Research Education and Mentoring Group (MICHR-EMG)
Study Objective	To clinically characterize the new burst spinal cord stimulation (Burst-SCS) therapy for chronic pain management. We will investigate the treatment effects of Burst-SCS and its underlying therapeutic mechanisms of action in chronic pain patients who have been deemed candidates for Burst-SCS therapy, and who have already been selected to receive a temporary externalized trial of Burst-SCS from their own doctors as part of their standard clinical care.
Study Design	
Randomized, double-blind, placebo-controlled, crossover study.
 
Subjects will participate in up to five research visits. During the first visit, we will screen chronic pain patients who have already been selected to receive a temporary externalized trial of Burst-SCS from their own doctors as part of their standard clinical care. During the second visit, we will perform pre-operative baseline assessment prior to implantation of the spinal cord stimulation (SCS) electrode arrays. Following lead implantation, and during the externalized “trial phase” of Burst-SCS, we will randomize subjects to receive either 24 hours of clinically-effective Burst-SCS followed by 24 hours of sham SCS or vice versa (crossover design). We will perform assessments before the start of the randomization (visit 3), and at the end of each 24-hour period (visits 4 and 5).
 
We will have two research teams. One team will be unblinded and will perform stimulator programming/adjustment, and the other team will be blinded and will perform clinical testing and collect study outcome measures.

Study Interventions	Burst-SCS and Sham SCS.
Study Duration	Subjects will participate in up to 5 research visits and each visit is expected to last about 2 hours. Therefore, the total time commitment for each subject is approximately 10 hours over 2-3 months .
Sample Size and Population	We will recruit 20 chronic pain patients who have been deemed candidates for Burst-SCS therapy, and who have already been selected to receive a temporary externalized trial of Burst-SCS from their own doctors as part of their standard clinical care.

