Statistical Analyses	We will perform appropriate statistical tests to look for significant differences between treatment effects on primary and secondary outcomes.

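### Section 8.3.1 builds the primary VAS analysis around implantation and does not state the period-adjusted, within-patient Burst-minus-sham contrast at visits 4 and 5

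*Combined protocol and SAP*

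**What the plan says.** Section 8.3.1 says VAS scores will be computed at "pre-implantation (visits 1 and 2) and post-implantation (visits 3,4 and 5) to help assess percentage change in pain scores". The sentence goes on to attribute that change to stimulation and names both Burst-SCS and sham SCS. For the questionnaires it continues in the same way: "we will assess outcomes of pain-specific questionnaires at pre-implantation and post-implantation, and compare across all patients using appropriate statistical tests". It gives no test, model, denominator or period term for the VAS.

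Other sections supply parts of the picture:

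- Section 5.1 (Aim 1): "we will compare the pain-relieving effects of Burst-SCS to sham (no) SCS", and "The primary outcome measure will be the change in patient-reported ratings of pain intensity".
- Synopsis, Statistical Analyses: tests will look for "significant differences between treatment effects on primary and secondary outcomes".
- Synopsis, Study Design: "assessments before the start of the randomization (visit 3), and at the end of each 24-hour period (visits 4 and 5").
- Section 6.1: "During the second visit, we will perform pre-operative baseline assessment in the subjects".
- Section 8.2.2, Table 1: "Primary outcome: VAS ratings".
- Section 2 (schedule): randomisation and the start of treatment both fall at the end of visit 3, and the VAS is listed as part of the SFMPQ.

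**The concern.** Only visits 4 and 5 follow randomised treatment. Section 8.3.1 instead divides the visits at implantation, which is not randomised, and puts visit 3 on the same side as visits 4 and 5. A fall in pain across that divide can come from the procedure, expectation, regression to the mean or the clinical programming that precedes the study phase. Section 3 gives control of placebo effects as the reason for the sham arm, so the primary analysis should rest on the comparison that provides that control.

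The tested quantity also appears in three forms: ratings (Table 1), change (5.1) and percentage change (8.3.1). Two analysts could follow the text and report different primary results from the same 20 patients. Nor is there any allowance for a difference between the first and second 24-hour period, which is a standard term in a two-period crossover.

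**Working it through.** **Stated figure.** Section 8.1 gives 20 patients with no effect size, SD, alpha or power, so there is nothing to reproduce. Every numerical input below other than n = 20 and the 0–100 mm scale is an assumption.

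**1. The text, side by side.** Section 5.1 gives the comparison (Burst versus sham). The synopsis and 6.1 give the end-of-period visits (4 and 5). Section 6.1 names visit 2 as baseline. The schedule ties the VAS to the SFMPQ. Section 8.3.1 does not combine these: it does not pair visits 4 and 5 within patient, say which visit is the denominator, or mention period.

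**2. What the literal reading would do.** Simulation of 20,000 trials with n = 20, pre-implantation mean 70 mm, between-patient SD 15, visit SD 12, no true Burst effect, and a non-specific fall at visits 3, 4 and 5. Rejection rates at two-sided 5%:

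| Non-specific fall | Pooled pre/post % change | Burst visit vs pre-implantation | Paired Burst − sham |
|---|---|---|---|
| 10 mm | 90% | 71% | 5% |
| 15 mm | 99.5% | 96% | 5% |
| 20 mm | 99.9% | 99.7% | 5% |

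**3. The period term.** Let D = Burst − sham within patient, δ the true effect, and π the period 2 minus period 1 shift. Patients given Burst first have mean D = δ − π; patients given sham first have δ + π. With n1 Burst-first and n2 sham-first patients and N = n1 + n2, the unadjusted mean of D has

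bias = π(n2 − n1)/N.

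For π = 10 mm:

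- 10/10: bias 0, but the spread of D rises from 20 to √(20² + 10²) = 22.4 mm.
- 12/8: 10 × 4/20 = 2 mm in size.
- 13/7: 10 × 6/20 = 3 mm in size.

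The adjusted estimate is the average of the two sequence means, with SE = ½ × 20 × √(1/n1 + 1/n2) on 18 df. For an effect of 15 mm:

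- 10/10: SE 4.47, 15/4.47 = 3.35, power 89%.
- 12/8: SE 4.56, 15/4.56 = 3.29, power 87.5%.

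Without the term (simulation, π = 10 mm):

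- 10/10: power 83%.
- 12/8: power 71% or 92%, depending on whether the bias shrinks or inflates the benefit; type I error 4.5%.
- 13/7: type I error about 6.5%.

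Under simple 1:1 randomisation, itself an assumption, a 12/8 or worse split has binomial probability 50%, and 13/7 or worse 26%. Blocking would remove most of this.

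**4. Cost of the term if π = 0.** The paired t-test on 19 df has power of about 89%. The adjusted test gives up about 0.2 points at 10/10, 1.5 at 12/8 and 3 at 13/7.

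**5. Scale.** Take Burst 35 mm and sham 50 mm. The difference is −15 mm whatever the baseline. As percentage change the contrast is −15/80 = −18.8, −15/70 = −21.4, −15/60 = −25.0 or −15/45 = −33.3 points. A percentage analysis is therefore defined only once one denominator, common to both periods, is named.

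**The case against.** The strongest reply is that the intent is plain. Section 8.3.1 itself names Burst-SCS and sham SCS, Aim 1 and the synopsis say they will be compared, and 6.1 places assessments at the end of each period. That stands as evidence of intent. A reader might infer from 8.3.1 that the trial will be judged by an uncontrolled pre/post test; the documents do not support that, and the 90% figure shows only what the literal wording would permit. What remains is that no section turns the intent into an analysis.

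Other stronger readings also fail:

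- **Percentage change is the wrong scale.** Not shown. No VAS SD or correlation is given, either scale can have more power depending on how noise and benefit behave, and 7.1.1 values comparison with the literature.
- **Visits 1 and 2 are pooled as baseline.** The text says scores are computed at those visits, not that they are averaged. The schedule also allows both visits on one day, in which case the two readings may differ little.
- **Two rival primary VAS readings.** The schedule and 7.1.2 place the VAS in the SFMPQ. Section 7.1.1 also mentions a post-QST VAS, but in saying where the scale is described. This needs clarification only.
- **Sequences will be unbalanced.** Section 6.4 leaves the randomisation plan to a biostatistician and states neither ratio nor blocking. Imbalance is possible, not shown.

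The wash-out argument in 6.1 concerns carry-over and does not cover a period effect. The outlier and transformation rule in 8.2.1 is a separate matter.

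**Conclusion.** The point holds as a gap between design and written analysis, and it should be fixed before unblinding. The design is sound and the needed readings are already scheduled, but 8.3.1 as worded does not use the randomised crossover comparison and has no period term. The gain from adjustment is moderate: about 6 power points (83% to 89%) at 10/10, and removal of a 2 mm bias at 12/8 or 3 mm at 13/7. These figures rest on an assumed 15 mm effect, 20 mm SD of differences and 10 mm period effect, none of which the documents give. With a smaller period effect the gain shrinks. The case for naming the contrast itself does not depend on those inputs.

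**What to change.** State in 8.3.1 that the primary analysis estimates the within-patient Burst-minus-sham difference in the SFMPQ VAS at the end of each 24-hour period (visits 4 and 5), adjusted for period, with a 95% CI. Either a two-sequence t-test or a mixed model with treatment and period fixed and patient random will do. With complete data they give the same estimate and SE. The mixed model needs small-sample t degrees of freedom, because a normal reference in place of t on 18 df would give 6.6% type I error. Keep visit 3 out of this contrast.

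Fix the scale in advance and align the word change in 5.1 with it. Millimetres need no baseline. Percentage change needs one common pre-randomisation denominator for both periods, for which visit 2 is the natural choice because the synopsis and 6.1 call it baseline. Report the other scale as supportive, and say that the post-QST VAS is not the primary reading.

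Use the same contrast for the other questionnaires and QST measures collected at visits 4 and 5. It cannot apply to HADS or EQ-5D, which the schedule collects only at visits 1 to 3.

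The cost is wording in 8.3.1 and one word in 5.1, with no new visits or data. If there is no period effect, the term costs the 0.2 to 3 power points shown above. If millimetres are chosen, comparison with published percentage relief rests on a supportive output.
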